1.0 Objectives

- To evaluate the ability of lenalidomide to improve the Hypogammaglobulinemia (achieve target IgG response) in patients with CLL.
- To evaluate the ability of lenalidomide to improve the protective antibody titers and serological responses specific to influenza and pneumococcal vaccination (seroconversion response).
- To evaluate the ability of lenalidomide to improve non IgG immune dysfunction such as T cells, cytokines and immunoglobulin subclasses.

2.0 Background

Chronic lymphocytic leukemia (CLL) is the most common adult leukemia. It arises from clonal and functionally incompetent B cells. Patients with CLL suffer from immunosuppression, predominantly due to hypogammaglobulinemia (IgG3 and IgG4), and infections are a common cause of morbidity and mortality among these patients [1]. Immunodeficiency in patients with CLL is complex and multifactorial involving defects in immunoglobulin secretion, T cell functions, complement cascade and neutrophil functions. Very few clinical studies have focused on strategies to overcome the humoral immunodeficiency associated with CLL [2]. Prophylactic antimicrobial therapy and/or intravenous immunoglobulins are often administered to patients with CLL who develop repeated infections. In patients requiring treatment, chemoimmunotherapy further compromises the immune system by decreasing T cell counts and worsening hypogammaglobulinemia. Thus there is a need for strategies which could correct the hypogammaglobulinemia and improve immune reconstitution in patients with CLL.

Streptococcus pneumoniae, *Haemophilus influenzae* type b (Hib) and influenza viruses are common causes of infections in patients with CLL [3]. Vaccinations for influenza and pneumococcus are recommended, but their effectiveness due to decreased antibody response to immunizations is questionable [4]. A prior study from our center [5] has shown that a 23-valent polysaccharide vaccine against pneumococcus does not mount an effective antibody response in 75% of patients with CLL even when multiple doses of GM-CSF are used concomitantly. Hypogammaglobulinemia is likely to further contribute to impaired vaccination responses in these patients [6]. Conjugation with immune adjuvants (like ranitidine) and conjugate vaccines with high valency were found helpful in mounting an effective antibody response to *Haemophilus influenzae* type B, but did not have an effect in the response to Influenza immunization [7],[8]. Thus immune strategies which could circumvent these issues are needed.

Lenalidomide is an immunomodulatory agent related to thalidomide. This oral agent induces clinical responses in patients with CLL. Its mode of action is pleiotropic, affecting the bone marrow and tumor microenvironments, angiogenesis, T cell immune synapse dysfunction, antibody production, regulatory T cells numbers and function and other unknown mechanisms. When patients with CLL received lenalidomide as initial treatment of their disease, improvement in serum levels of immunoglobulins (IgG, IgA and IgM) was observed in a subset of patients [9]. We demonstrated that out of 16 patients who had low IgG level (<700 mg/dL) before therapy, 8 patients (50%) showed a normalization of IgG after 15 cycles and another 3 (19%) showed a rise in IgG of >50% from that of baseline. [9]. In a parallel study from the same patient cohort, we showed that treatment with lenalidomide was also followed by normalization of T cell number

and function [10]. Lapalombella and colleagues have also shown that lenalidomide can enhance CD154 expression on CLL cells and enhance antibody producing ability of B cells in vitro and ex vivo further supporting our hypothesis that lenalidomide could have a positive immunomodulatory effect in patients with CLL [11].

Therefore, we propose to conduct a single arm prospective clinical trial to assess the efficacy of lenalidomide in improving immunoglobulin levels and to potentiate antibody responses to immunizations with influenza and pneumococcal vaccination in patients with CLL.

A low dose of lenalidomide, 5 mg, will be administered three times a week with the plan to escalate to daily dosing in the case of no response. The rationale for the low dose is the potential to obtain an immunoresponse while avoiding the risk for myelosuppression. In our previous experience increase in immunoglobulin levels were seen in patients receiving lenalidomide, 5 mg every-other-day.

3.0 Treatment Plan

We will administer lenalidomide at the dose of 5 mg/day on Monday, Wednesday and Friday for 3 months. If IgG levels improve by at least 25% of baseline, we will continue lenalidomide administration 3 months on and 3 months off for 2 years. If IgG levels do not improve we will increase the frequency of lenalidomide to 5 mg/day for additional 3 months and if response is achieved, lenalidomide will be continued at 5mg/day 3 month on/3 month off for a total of 2 years. Seasonal influenza vaccination (*Trivalent Influenza Vaccine, Fluarix, quadrivalent*) will be administered yearly, during the fall/winter season and pneumococcal immunization (Pneumococcal Polysaccharide Vaccine, Pneumovax)

will be administered once between month 6 and month 21. Patients, who have received the Pneumovax vaccine within last 5 years, will not receive Pneumovax vaccination.

Serum levels of all the immunoglobulin subclasses will be measured at baseline and every 3 months (+/- 3 weeks) during therapy. Serum levels of antipneumococcal capsular polysaccharide antibodies will be measured before, 4 weeks (+/- 2 week) and 3 months (+/- 3 weeks) after pneumococcal vaccination and at end of the study (to assess sustainable antibody responses) by ELISA. Haemagglutination inhibition antibody titres (HAI) will be assessed by WHO influenza reagent kit, before vaccination, 4 weeks (+/- 2 week) and 3 months (+/- 3 weeks) after influenza vaccination [12]. Influenza specific quantitative and qualitative CD8+ and CD4+ T cell responses will be determined by multiparameter flow cytometry technique from stored PBMC's from the patients before vaccination, 4 weeks (+/- 2 week) and 3 months (+/- 3 weeks) after influenza vaccination and at the end of the study [13, 14].

Dosage form

Lenalidomide will be supplied by Celgene Corporation as 2.5mg and 5mg capsules for oral administration.

Prescribing Information

Lenalidomide (Revlimid®) will be provided to research subjects for the duration of their participation in this trial at no charge to them or their insurance providers. Lenalidomide will be provided in accordance with the Celgene Corporation's Revlimid REMS® program. Per standard Revlimid REMS® program requirements, all physicians who prescribe lenalidomide for research subjects enrolled into this trial, and all research subjects enrolled into this trial, must be registered in, and must comply with, all requirements of the Revlimid REMS® program.

Only enough lenalidomide for one cycle of therapy will be supplied to the patient each cycle.

Pregnancy Testing

Must follow pregnancy testing requirements as outlined in the Revlimid REMS® prDose modification for lenalidomide:

Table 1: Dose Modification Guidelines for Lenalidomide

NCI CTC Toxicity Grade	Action
Grade 3 neutropenia associated with fever (temperature >38.5o C) or Grade 4 neutropenia (ANC <500/mm ³ , or ≤75% of baseline)*.	1) Hold (interrupt dose). 2) Follow CBC weekly until resolution or stabilization 3) If neutropenia has resolved to ≤ grade 2, implement dose reduction and continue therapy.
Thrombocytopenia Grade 4 (platelet count ≤ 25,000/mm ³) or ≤ 75% of baseline.*	1) Hold (interrupt dose). 2) Follow CBC weekly until resolution or stabilization 3) If thrombocytopenia resolves to ≤ grade 2, implement dose reduction and continue therapy.
Non-blistering rash Grade 3	1) If grade 3, hold (interrupt) dose. Follow weekly until resolution or stabilization. 2) If the toxicity resolves to ≤ grade 1, implement dose reduction and continue therapy.
Grade 4	1) Discontinue lenalidomide study drug.
Desquamating (blistering) rash-any Grade	Discontinue lenalidomide study drug.
Erythema multiforme - Grade 3	Discontinue lenalidomide study drug.
Neuropathy Grade 3	1) If grade 3, hold (interrupt) dose. Follow weekly until resolution or stabilization. 2) If the toxicity resolves to ≤ grade 2, implement dose reduction and continue therapy.
Grade 4	Discontinue lenalidomide study drug.
Sinus bradycardia/other cardiac arrhythmia Grade 2	1) Hold (interrupt dose). Follow at least weekly until resolution or stabilization. 2) If the toxicity resolves to <grade 1, implement dose reduction and continue therapy.
≥ Grade 3	Discontinue lenalidomide study drug.

Allergic reaction or hypersensitivity Grade 3
 
Grade 4
	
1) Hold (interrupt dose). Follow at least weekly until resolution or stabilization 2) If the toxicity resolves to <grade 1, implement dose reduction and continue therapy.
 
Discontinue lenalidomide study drug.

Venous thrombosis/embolism ≥Grade 3
	
Hold (interrupt) dose and start anticoagulation; restart at investigator's discretion (maintain dose level).

Hepatic or other non-hematologic toxicity assessed as lenalidomide-related ≥ Grade 3
	
1) Hold (interrupt) dose. Follow at least weekly until resolution or stabilization. 2) If the toxicity resolves to <grade 2, implement dose reduction and continue therapy.


Tumor flare refractory to oral pain meds
	
Hold dose and differentiate tumor flare from progression. Restart therapy at the investigator's discretion.

*The use of cytokine support and/or transfusions to maintain adequate blood neutrophil and platelet counts may be considered at the investigator's discretion.

Dose reduction consists of 2.5 mg/daily.

Anticoagulation Consideration

Lenalidomide increases the risk of thrombotic events in patients who are at high risk or who have a history of thrombosis in particular when combined with other drugs known to cause thrombosis. When lenalidomide is combined with other agents such as steroids, e.g. dexamethasone and prednisone, and Adriamycin or daunorubicin the risk of thrombosis is increased. Treating physicians may consider the use of aspirin or low molecular weight heparin in patients at high risk for thrombotic events.

Recommended Concomitant Therapy

Subjects should receive full supportive care, including transfusions of blood and blood products, antibiotics, and antiemetics when appropriate. Use of filgrastim (G-CSF), to

treat for neutropenia is permitted while on study. Use of erythropoiesis stimulating agent is strongly discouraged.

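### The only dose-reduction rule names no dosing days, so on the starting three-times-weekly schedule its literal reading raises the weekly dose after toxicity (15 to 17.5 mg)

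*Protocol*

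**What the plan says.** The starting regimen is in Protocol 3.0 Treatment Plan: "We will administer lenalidomide at the dose of 5 mg/day on Monday, Wednesday and Friday for 3 months". If IgG has improved enough at 3 months, "we will continue lenalidomide administration 3 months on and 3 months off for 2 years"; no change of dosing days is stated. If it has not, "we will increase the frequency of lenalidomide to 5 mg/day for additional 3 months".

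Table 1 in the same section sets out dose modification. Seven of its rows hold the drug, wait for recovery to a named grade and then restart at a reduced dose: neutropenia, thrombocytopenia, grade 3 non-blistering rash, grade 3 neuropathy, grade 2 arrhythmia, grade 3 allergic reaction, and hepatic or other non-hematologic toxicity. The reduced dose itself appears once, in a line below the table: "Dose reduction consists of 2.5 mg/daily". There is no entry by schedule and no list of dosing days. The SAP carries only the statistical section and does not address dosing.

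**The concern.** A dose-reduction line should lead every prescriber to the same prescription. This one gives the amount (2.5 mg) but not the days, and the Protocol's own usage supports two readings. In 3.0 the starting regimen is written per day and then limited to three weekdays, so a daily amount can mean the amount per dosing day. But the step-up in 3.0 uses the same per-day form, with no weekdays, to mean every day. Protocol 2.0 Background also contrasts the two schedules directly: the drug "will be administered three times a week with the plan to escalate to daily dosing in the case of no response". There, daily means seven days a week.

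This matters for patients on the starting schedule, which means everyone in the first 3 months and 3-month responders afterwards. On the every-day reading, a patient held for toxicity restarts on a higher weekly dose than the one that preceded the toxicity. That runs against the reason given for the regimen in 2.0: "The rationale for the low dose is the potential to obtain an immunoresponse while avoiding the risk for myelosuppression". For neutropenia and thrombocytopenia, restart needs recovery only to grade 2 or lower, so counts may still be reduced at that point.

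**Working it through.** The documents state no weekly totals, so there is no figure of the plan's own to reproduce.

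**Inputs**, all from Protocol 3.0 Treatment Plan:
- Starting schedule: 5 mg, 3 days a week
- Escalated schedule: 5 mg, 7 days a week
- Reduced dose: 2.5 mg, days not stated
- Capsules: "Lenalidomide will be supplied by Celgene Corporation as 2.5mg and 5mg capsules for oral administration", so either reading can be dispensed

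**Formula:** weekly dose = mg per dosing day × dosing days per week.

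| Regimen | Weekly dose | Change from the patient's prior dose |
|---|---|---|
| Start | 5 × 3 = 15 mg | – |
| Reduced from start, same three days | 2.5 × 3 = 7.5 mg | 7.5/15 = 0.50, −50% |
| Reduced from start, every day | 2.5 × 7 = 17.5 mg | 17.5/15 = 1.167, +16.7% |
| Escalated | 5 × 7 = 35 mg | – |
| Reduced from escalated, every day | 2.5 × 7 = 17.5 mg | 17.5/35 = 0.50, −50% |

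On the starting schedule the two readings differ by 17.5 − 7.5 = 10 mg a week, a ratio of 17.5/7.5 = 2.33. That ratio compares one reading with the other. The excess over the planned dose is the 16.7%.

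**How far exposure could rise on the every-day reading.** Two assumptions are needed, because the documents give neither figure: a 3-month block is taken as 13 weeks, and the length of the hold is varied. An unreduced block is 15 × 13 = 195 mg. With *h* weeks held and *r* weeks at the reduced dose, the block total differs from 195 mg by 2.5*r* − 15*h*. The worst case is toxicity at the very start of the block, so that *r* = 13 − *h*.

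- 1-week hold: 17.5 × 12 = 210 mg, +15 mg
- 2-week hold: 17.5 × 11 = 192.5 mg, −2.5 mg
- Break-even: 2.5(13 − *h*) = 15*h*, so *h* = 32.5/17.5 = 1.857 weeks, or 13 days

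In the block where toxicity occurs, any hold longer than 13 days therefore leaves the total below the unreduced one. The full contrast appears only in a later 13-week block with no hold: 17.5 × 13 = 227.5 mg (every day) or 7.5 × 13 = 97.5 mg (same three days), against 195 mg unreduced.

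**The case against.** The best reply is that context settles the intent. Section 3.0 treats dose and frequency as separate things: the step-up is described as a change in frequency, so a dose reduction should halve the dose and leave the days alone. A reduction that moves a patient from three to seven dosing days after toxicity, and raises the weekly total, would contradict both the word itself and the stated rationale. Most clinicians would probably halve the capsule and keep the days. The Protocol also refers to a single center and dispenses one cycle at a time, which makes divergent prescribing less likely.

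Much of this stands. The same-days reading is the likely intent, and a reader who inferred that the plan means to raise the dose after toxicity would go further than the text allows. Nor is the reduced dose absent: an amount is given, and only the days are missing. What does not follow is that the line is clear. The every-day reading also halves each single dose, so halving does not identify the schedule. It is also the literal sense of the words, and it matches how 2.0 uses daily dosing.

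The second reply is that harm is small. That is fair. Restart follows a hold and recovery to the grade named in the row, 17.5 mg a week is half of what the Protocol uses on escalation, and a moderate hold offsets the increase in the block concerned. This limits the severity but does not remove the ambiguity.

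**Conclusion.** The point holds as a dosing-safety ambiguity that should be fixed. For patients on 5 mg Monday/Wednesday/Friday, the single reduction rule can be followed to 7.5 mg a week (−50%, probably intended) or 17.5 mg a week (+16.7%, the literal wording). For patients on 5 mg every day it is an unambiguous 50% cut.

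The weekly figures rest only on doses and days stated in the Protocol. The block totals rest on the assumed 13-week block and hold lengths, and serve only to show that harm on the adverse reading is bounded. The documents give no rate for the toxicities that trigger a reduction, so the number of patients affected cannot be estimated.

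A reader might infer that the ambiguity undermines the trial's statistical design. The documents do not support that: the sample size, error rates and endpoint definitions do not depend on the reduced dose.

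**What to change.** Replace the line below Table 1 with one entry per schedule:

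- Patients on 5 mg Monday/Wednesday/Friday: reduce to 2.5 mg Monday/Wednesday/Friday (7.5 mg a week).
- Patients on 5 mg every day: reduce to 2.5 mg every day (17.5 mg a week).

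The clinical team should confirm both values, since the first rests on likely intent and not on an explicit statement. The cost is one line of text per schedule in an amendment, with no extra patients or visits and no new capsule strength.

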4.0 Patient Eligibility

Inclusion criteria:

1. Chronic lymphocytic leukemia (CLL) patients with IgG less than 500 mg/dl with/without symptoms who are either untreated or previously treated, regardless of response, at least 6 months from prior therapy (including mAb).
2. ECOG/WHO performance status of 0-2.
3. Adequate renal functions as indicated by serum creatinine ≤ 2 mg/dl.
4. Adequate hepatic function indicated as total bilirubin ≤ 2 mg/dl and ALT \leq two times the upper limit of normal.
5. Disease free of prior malignancies for 3 years with exception of currently treated basal cell, squamous cell carcinoma of the skin, or carcinoma "in situ" of the cervix or breast. Patients with malignancies with indolent behavior such as prostate cancer treated with radiation or surgery can be enrolled in the study as long as they have a reasonable expectation to have been cured with the treatment modality received.
6. Females of childbearing potential (FCBP). A female of childbearing potential is a sexually mature woman who: 1) has not undergone a hysterectomy or bilateral oophorectomy; or 2) has not been naturally postmenopausal for at least 24 consecutive months (i.e., has not had menses at any time in the preceding 24 consecutive months).

7. FCBP must have a negative serum or urine pregnancy test with a sensitivity of at least 50 mIU/mL within 10 – 14 days prior to and again within 24 hours of starting lenalidomide and must either commit to continued abstinence from heterosexual intercourse or begin **TWO** acceptable methods of birth control, one highly effective method and one additional effective method **AT THE SAME TIME**, at least 28 days before she starts taking lenalidomide.
8. FCBP must also agree to ongoing pregnancy testing (weekly for the first four weeks and then every 28 days while on therapy and at discontinuation of treatment).
9. Men must agree to use a latex condom during sexual contact with a FCBP even if they have had a successful vasectomy. All patients must be counseled at a minimum of every 28 days about pregnancy precautions and risks of fetal exposure.
10. Patients must be 18 years of age or older.
11. All study participants must be registered into the mandatory Revlimid® program, and be willing and able to comply with the requirements of Revlimid®.
12. Females of reproductive potential must adhere to the scheduled pregnancy testing as required in the Revlimid REMS® program. Able to take aspirin (81 or 325 mg) daily as prophylactic anticoagulation (patients intolerant to ASA may use warfarin or low molecular weight heparin).
- 13.

Exclusion criteria

1. Known sensitivity to lenalidomide or other thalidomide derivatives.

2. History of Guillain-Barre within 6 weeks of previous influenza vaccination
3. Patient on steroids therapy.
4. Documented polymphocytic leukemia (polymphocytes more than 55% in the blood) or Richter's transformation.
5. Known positivity for HIV or active hepatitis (B or C).
6. Pregnant or breast feeding females.
7. History of tuberculosis treated within the last five years or recent exposure to tuberculosis.
8. Any serious medical condition, laboratory abnormality, or psychiatric illness that places the subject at unacceptable risk if he/she were to participate in the study.
9. Patients with a recent history of deep vein thrombosis (DVT) or pulmonary embolus (PE), in six months prior to enrollment are not eligible for this study.
10. Subjects who have currently active hepatic or biliary disease (with exception of patients with Gilbert's syndrome).
11. Patients with severe allergic reaction (e.g., anaphylaxis) after previous dose of any influenza vaccine or to a vaccine component, including egg protein.
12. Moderate or severe acute illness with or without fever.
13. Use of any other experimental drug or therapy within 28 days of baseline.
14. Concurrent use of other anti-cancer agents or treatments.

5.0 Pretreatment evaluation

Within 7 days (+/- 4 days) prior to start of treatment, patients should have a history and physical examination. Electrocardiogram (ECG), CBC with differential and serum chemistry tests (sodium, potassium, calcium, magnesium, phosphorus, BUN, creatinine,

glucose, and albumin, total proteins, alkaline phosphatase, total bilirubin, ALT, uric acid). Serum beta-2-microglobulin and IgA, IgG, IgM levels. Serum levels of all the immunoglobulin subclasses will be measured at the baseline (+/- 4 days). T-cell lymphocyte number and T-cell subsets, CD4+, CD8+ will be measured baseline. Serum samples for cytokine levels (properdin, IFN- γ , IL-10, TNF- α , BAFF, IL-8, CCL3, and CCL4) will be stored at baseline. Pregnancy tests for females of childbearing potential and Risks of Fetal Exposure, Pregnancy Testing Guidelines and Acceptable Birth Control Methods will be discussed.. .

6.0 Evaluation during the Study

Complete blood counts (white blood cell, hemoglobin, platelets and differential), serum chemistry, basic metabolic profile, (sodium, potassium, chloride, CO₂, BUN, creatinine and glucose) will be monitored once every two-four weeks (+/- 4 days) while on lenalidomide.

At 3 months (+/- 3 weeks), patients will have a physical examination, CBC with differential and chemical survey, serum beta-2-microglobulin and IgA, IgG, IgM levels, flow cytometry (CD4+, CD8+). Pregnancy tests for females of childbearing potential and Risks of Fetal Exposure, Pregnancy Testing Guidelines and Acceptable Birth Control Methods, will be discussed with the patients.

Pneumococcal vaccination: Serum levels of antipneumococcal capsular polysaccharide antibodies will be measured before, 4 weeks (+/- 2 week) and 3 months (+/- 3 weeks) after vaccination and at the end of the study (to assess sustainable antibody responses) by ELISA. Influenza vaccination: Haemagglutination inhibition antibody titres (HAI) will be assessed by WHO influenza reagent kit before, 4 weeks (+/- 2 week) and 3 months

(+/- 3 weeks) after vaccination and at end of the study (to assess sustainable antibody responses) [12]. Influenza specific quantitative and qualitative CD8+ and CD4+ T cell responses will be determined by multiparameter flow cytometry techniques from stored PBMC's from the patients before vaccination, 4 weeks (+/- 2 week) and 3 months (+/- 3 weeks) after vaccination [13, 14]. Serum samples for cytokine levels (properdin, IFN- γ , IL-10, TNF- α , BAFF, IL-8, CCL3, and CCL4) will be stored before influenza vaccination at 4 weeks (+/- 2 week), 3 months (+/- 3 weeks) and at the end of the study). PBMC's will be stored at baseline, 4 weeks (+/- 2 week) and 3 months (+/- 3 weeks) after influenza vaccination to determine by multiparameter flow cytometry technique changes in influenza specific quantitative (using HLA-A2 restricted FluMP pentamer) and qualitative (using CD107a, IFN-gamma, IL-2 and TNF-alpha by intracellular staining) CD8+ and CD4+ T cell responses, as described [15].

Criteria for study discontinuation:

Treatment with study drug is discontinued and the patient will be removed from study when any of the following occurs:

1. Lack of response
2. Adverse event(s) that in the judgment of the investigator or the patient may cause severe or permanent harm or which rule out continuation of the study drug
3. Withdrawal of consent
4. Lost to follow-up
5. Suspected pregnancy

